7.2.3. Vital Signs

Vital sign measurements (including oxygen saturation, oral temperature, respiratory rate, and supine BP and pulse rate) will be obtained at the timepoints specified in Appendix 4.

Blood pressure and pulse rate measurements should be performed using the same arm for each reading and measurements should be taken after the subject has been resting in the supine position for at least 5 minutes.

When vital sign measurements are scheduled at the same time as blood draws, the blood draws will be obtained at the scheduled timepoint, and the vital sign measurements will be obtained prior to and as close as possible to the scheduled blood draw.

7.2.4. 12-Lead Electrocardiogram

A 12-lead ECG (including HR, PR, RR, QRS, and QT interval parameters) will be obtained after the subject has been resting for at least 10 minutes in the supine position at the timepoints specified in Appendix 4. The QT interval will be corrected for heart rate by Fridericia's (QTcF = $QT/[RR]^{1/3}$) formula.

When 12-lead ECGs are scheduled at the same time as blood draws, the blood draws will be obtained at the scheduled timepoint, and the 12-lead ECGs will be obtained prior to and as close as possible to the scheduled blood draw.

7.2.5. Physical Examination

A complete or abbreviated physical examination will be performed at the timepoints specified in Appendix 4. Complete physical examinations will evaluate general appearance and the following body systems/organs: dermatological; head and eyes; ears, nose, mouth, and throat; pulmonary; cardiovascular; abdominal; lymphatic; musculoskeletal/extremities; and neurological. Weight and height will be reported (height only reported during Screening).

Abbreviated physical examinations will evaluate general appearance and the following body systems/organs: dermatological; pulmonary; cardiovascular; abdominal; and neurological.

8. SAMPLE SIZE AND DATA ANALYSIS

8.1. Determination of Sample Size

No formal statistical assessment of sample size has been conducted as this study does not have a hypothesis. The sample size chosen for this study is common in human radiolabeled studies and is considered sufficient to achieve the objectives of the study. Six subjects will participate in each part of the study. Each subject will participate in either Part 1 or Part 2. In the event of early withdrawal of any subjects and/or to ensure 6 subjects complete each part of the study, replacement subjects may be enrolled at the discretion of the Sponsor.

8.2. Analysis Populations

8.2.1. Pharmacokinetic Population

The **PK population** will include all subjects who received at least 1 dose of LOXO-305 or $[^{14}C]$ -LOXO-305 and have evaluable PK data. At the discretion of the Sponsor, a subject may be excluded from the PK summary statistics and statistical analysis. The impact of protocol deviations on PK population will be evaluated on a case-by-case basis.

8.2.2. Safety Population

The **safety population** will include all subjects who received at least 1 dose of LOXO-305. Subjects will be classified into groups based on actual treatment received.

8.3. Pharmacokinetic Analyses

Part 1

Samples for determination of LOXO-305 concentrations in plasma, total radioactivity concentrations in plasma, whole blood, urine, and feces, and for metabolite profiling/characterization will be obtained through at least 264 hours postdose (Day 12), and possibly up to 504 hours postdose (Day 22). Pharmacokinetic parameters (where applicable) will be calculated using standard noncompartmental methods.

Whenever possible, the following PK parameters will be calculated for each subject, based on the plasma concentrations of LOXO-305 and whole blood and plasma concentrations of total radioactivity:

AUC _{0-inf}	area under the concentration-time curve from time 0 extrapolated to infinity, calculated using the formula: $AUC_{0-inf} = AUC_{0-t} + (C_{last} \div \lambda_z)$ where C_{last} is the last quantifiable concentration and λ_z is the apparent terminal elimination rate constant
AUC _{0-t}	area under the concentration-time curve from hour 0 to the last measurable concentration, calculated using the linear trapezoidal rule for increasing and decreasing concentrations
Cmax	maximum observed concentration

t _{max}	time to maximum observed concentration
t _{1/2}	apparent terminal elimination half-life (whenever possible), where $t^{1\!/_2}$ = ln(2)/ λ_z
CL/F	apparent systemic clearance (LOXO-305 only)
V _z /F	apparent volume of distribution during the terminal phase (LOXO-305 only)
AUC _{0-inf} Plasma LOXO-305/Total Radioactivity Ratio	AUC _{0-inf} of plasma LOXO-305 relative to AUC _{0-inf} of plasma total radioactivity
AUC _{0-inf} Blood/ Plasma Ratio	AUC _{0-inf} of whole blood total radioactivity to AUC _{0-inf} of plasma total radioactivity

Whenever possible, the following PK parameters will be calculated for each subject based on the urine concentrations of total radioactivity:

A _{eu}	amount excreted in urine per sampling interval
cumulative A _{eu}	cumulative amount excreted in urine
feu	percentage of dose excreted in urine per sampling interval, where $\% f_{eu} = 100 (A_{eu}/dose)$
cumulative f _{eu}	cumulative percentage excreted in urine

Whenever possible, the following PK parameters will be calculated for each subject based on the fecal concentrations of total radioactivity:

Aef	amount excreted in feces per sampling interval
cumulative Aef	cumulative amount excreted in feces
\mathbf{f}_{ef}	percentage of dose excreted in feces per sampling interval, where $\% f_{ef} = 100 (A_{ef}/dose)$
cumulative fef	cumulative percentage excreted in feces

Additionally, the metabolic profile of LOXO-305 and the identification of LOXO-305 metabolites will be determined for each subject. Pharmacokinetic parameters for relevant metabolites of LOXO-305 may be calculated for each subject in Part 1, as deemed appropriate, based on plasma, urine, and/or fecal concentration levels.

Part 2

Samples for determination of LOXO-305 concentrations in plasma, and total radioactivity and [¹⁴C]-LOXO-305 concentrations in plasma, urine, and feces will be obtained through 192 hours postdose (Day 9).

Pharmacokinetic parameters (where applicable) will be calculated using standard noncompartmental methods.

Whenever possible, the following PK parameters will be calculated for each subject, based on the plasma concentrations of $[^{14}C]$ -LOXO-305, LOXO-305, and total radioactivity:

AUC _{0-inf}	area under the concentration-time curve from time 0 extrapolated to infinity, calculated using the formula described above
AUC _{0-t}	area under the concentration-time curve from hour 0 to the last measurable concentration, calculated as described above
C _{max}	maximum observed concentration
t _{max}	time to maximum observed concentration
t _{1/2}	apparent terminal elimination half-life (whenever possible), where $t^{1\!\!/_2}$ = ln(2)/ λ_z
CL/F	apparent systemic clearance (LOXO-305 only)
V _z /F	apparent volume of distribution during the terminal phase (LOXO-305 only)
F	absolute bioavailability, calculated using the formula:
	$F = \frac{AUC_{0-inf}(oral) \times Dose (IV)}{AUC_{0-inf}(IV) \times Dose (oral)}$
CL	total clearance ([¹⁴ C]-LOXO-305 only)
Vz	volume of distribution ([¹⁴ C]-LOXO-305 only)
V _{ss}	volume of distribution at steady state ([¹⁴ C]-LOXO-305 only)

In addition, whenever possible, the following PK parameters will be calculated for each subject based on the urine concentrations of [¹⁴C]-LOXO-305 and total radioactivity:

Aeu	amount excreted in urine
cumulative A _{eu}	cumulative amount excreted in urine
feu	percentage of dose excreted in urine, calculated as described above

cumulative feu	cumulative percentage excreted in urine
CLR	renal clearance ([¹⁴ C]-LOXO-305 only)

Whenever possible, the following PK parameters will be calculated for each subject, based on the fecal concentrations of $[^{14}C]$ -LOXO-305 and total radioactivity:

Aef	amount excreted in feces
cumulative A _{ef}	cumulative amount excreted in feces
fef	percentage of dose excreted in feces, calculated as described above
cumulative fef	cumulative percentage excreted in feces

Pharmacokinetic calculations will be performed using commercial software such as Phoenix[™] WinNonlin[®] Version 8.1 or higher (Certara USA Inc.).

Other parameters may be added as appropriate. Final PK parameters reported will be detailed in the Statistical Analysis Plan (SAP).

Pharmacokinetic analysis will use actual times as recorded on the eCRF. All statistical analysis will be performed using SAS[®] Version 9.4 or greater. More details on the analyses will be included in the SAP.

8.3.1. Descriptive Analysis

Plasma and whole blood concentrations and PK parameters will be summarized with descriptive statistics (number, arithmetic mean, standard deviation, coefficient of variation [CV%], geometric mean, geometric CV%, median, minimum, and maximum).

Individual and mean plasma concentration-time curves (both linear and log linear) will be included in the final report.

8.3.2. Statistical Methodology

No formal statistical analyses are planned.

8.4. Safety Analysis

All safety assessments, including AEs and SAEs, vital sign measurements, clinical laboratory results, physical examination results, concomitant medications, and 12-lead ECGs, will be tabulated and summarized, where possible, using descriptive methodology, as needed, by timepoint. Unless otherwise specified, baseline value is defined as the last non-missing measurement before administration of LOXO-305 in each part. No formal statistical analyses are planned for the safety data. All safety data will be listed by subject.

Concomitant medications will be coded using the World Health Organization (WHO) Drug Dictionary (WHO Drug Global B3, September 2019 or higher). Adverse events will be coded

using MedDRA Version 22.1 (or higher). The incidence of AEs will be presented by severity and by relationship to study drug as determined by the Investigator or designee (Appendix 1 for AE reporting). All TEAEs will be summarized by SOC and PT.

8.5. Data Handling and Record Keeping

Any changes to information in the trial progress notes and other source documents will be initialed and dated on the day the change is made by a CRU staff member authorized to make the change. Changes will be made by striking a single line through erroneous data and clearly entering the correct data (eg, wrong data right data). If the reason for the change is not apparent, a brief explanation for the change will be written adjacent to the change by the clinician.

The Data Management Plan will be approved by the Sponsor.

Data will be validated during data entry by the CRU and verified by the Study Monitor. Data will then be reviewed by the data management group to resolve any outstanding issues. Listings will be generated after the database is cleaned by data management and will be reviewed by the Covance scientific team. The eCRF and ancillary data will be converted into final SAS[®] datasets following Study Data Tabulation Model or client-provided specifications. The final datasets structure will be verified using Web Submission Data Manager[®], while the dataset content will be peer reviewed by an independent programmer.

The tables, figures, and listings (TFLs) will be programmed per the final SAP. All TFLs will be peer reviewed by an independent programmer. In addition, draft TFLs will be reviewed by the Covance scientific team during the dry run and data review meetings.

The peer review will be performed by independent programmers following the quality control process and programming checklists.

8.6. Quality Control and Quality Assurance

Quality control and quality assurance will be performed according to Covance standard operating procedures or per client request, and as applicable, according to the contract between Covance and the Sponsor.

9. ADMINSTRATIVE ASPECTS

9.1. Change in Protocol

There will be no alterations in the protocol without agreement between the Sponsor and the Investigator (or designee).

There will be no alterations in the protocol affecting subject safety without the express written approval of the Sponsor, Investigator (or designee), and the IRB (see Form FDA 1572).

9.2. Site Initiation Visit/Investigator Meeting

Prior to the start of the clinical study, the representative(s) of the Sponsor will meet with the Investigator (or designee) and appropriate CRU staff to familiarize the Investigator (or designee) and CRU staff with the materials necessary for conducting the clinical study.

9.3. Disclosure

All information provided regarding the study, as well as all information collected/documented during the study, will be regarded as confidential. The Investigator (or designee) agrees not to disclose such information in any way without prior written permission from the Sponsor.

Any publication of the results, in part or in total (eg, articles in journals or newspapers, oral presentations, abstracts) by the Investigator (or designee) or their representative(s), shall require prior notification and review, within a reasonable timeframe, by the Sponsor, and cannot be made in violation of the Sponsor's confidentiality restrictions or to the detriment of the Sponsor's intellectual property rights.

9.4. Monitoring

The Sponsor will designate a Study Monitor who will be responsible for monitoring this clinical trial. The Sponsor's Study Monitor will monitor the study conduct, proper eCRF and source documentation completion and retention, and accurate study drug accountability. To this end, the Sponsor's Study Monitor will visit the CRU at suitable intervals and be in frequent contact through verbal and written communication. It is essential that the Sponsor's Study Monitor has access to all documents (related to the study and the individual participants) at any time these are requested. In turn, the Sponsor's Study Monitor will adhere to all requirements for subject confidentiality as outlined in the ICF. The Investigator (or designee) and Investigator's staff will be expected to cooperate with the Sponsor's Study Monitor, to be available during a portion of the monitoring visit to answer questions, and to provide any missing information.

9.5. Institutional Review Board

In accordance with US Title 21 CFR 56, the protocol, advertisement, ICF, and other information provided to subjects will be reviewed and approved by the IRB. The Sponsor will supply relevant material for the Investigator (or designee) to submit to the IRB for the protocol's review and approval. Verification of the IRB unconditional approval of the protocol and the written ICF statement will be transmitted to the Investigator (or designee).

The IRB will be informed by the Investigator (or designee) of subsequent protocol amendments and of serious and unexpected AEs. Approval for protocol amendments will be transmitted in writing to the Investigator (or designee). If requested, the Investigator (or designee) will permit audits by the IRB and regulatory inspections by providing direct access to source data/documents.

The Investigator (or designee) will provide the IRB with progress reports at appropriate intervals (not to exceed 1 year) and a Study Progress Report following the completion, termination, or discontinuation of the Investigator's (or designee's) participation in the study.

9.6. Informed Consent

Written informed consent for the study will be obtained from all subjects before protocol-specific procedures are carried out. The ICF will be approved (along with the protocol) by the IRB and will be acceptable to the Sponsor.

The Investigator (or designee) will explain the nature of the study and the action of the test product. The subjects will be informed that participation is voluntary and that they can withdraw from the study at any time. In accordance with 21 CFR 50, the informed consent process shall be documented by the use of a written ICF approved by the IRB and signed by the subject prior to protocol-specific procedures being performed.

The subject will sign 2 copies of the ICF. One copy will be given to the subject, and the other will be maintained with the subject's records.

9.7. Records

The results from data collected at Screening and during the study will be recorded in the subject's eCRF. To maintain confidentiality, the subjects will be identified only by numbers.

The completed eCRFs will be transferred to the Sponsor (or designee). Copies of each eCRF will be retained by the Investigator (or designee). All source documents, records, and reports will be retained by the CRU in accordance with 21 CFR 312.62(c).

All primary data, or copies thereof (eg, laboratory records, eCRFs, data sheets, correspondence, photographs, and computer records), which are a result of the original observations and activities of the study and are necessary for the reconstruction and evaluation of any study report, will be retained in the CRU archives.

9.8. Reference to Declaration of Helsinki/Basic Principles

The study procedures outlined in this protocol will be conducted in accordance with the US CFR governing Protection of Human Subjects (21 CFR 50), Financial Disclosure by Clinical Investigators (21 CFR 54), IRBs (21 CFR 56), Investigational New Drug Application (21 CFR 312), Applications for FDA Approval to Market a New Drug (21 CFR 314), and Radioactive Drugs for Certain Research Uses (21 CFR 361.1), as appropriate. As such, these sections of US Title 21 CFR, along with the applicable International Council for Harmonisation (ICH) Guidelines, are commonly known as Good Clinical Practices (GCP), which are consistent with the Declaration of Helsinki.

9.9. Financing and Insurance

Financing and insurance will be addressed in a separate agreement.

11. APPENDICES

Appendix 1: Adverse Event Reporting

Adverse Events

Definition of Adverse Events

An AE (or adverse experience) is defined as any untoward medical occurrence experienced by a patient or healthy adult subject, whether or not considered drug-related by the Investigator (or designee). A TEAE is an AE that starts on or after the first administration of study drug.

The following are all AEs:

- unfavorable changes in general condition;
- subjective or objective signs/symptoms;
- concomitant diseases or accidents;
- clinically relevant adverse changes in laboratory parameters observed in a subject during a clinical study.

Adverse events comprise all disturbances of general health status, subjective and objective disease symptoms (including laboratory abnormalities that are deemed clinically significant by the Investigator [or designee]), and accidents observed in the context of a clinical trial, irrespective of a possible causal relationship with the administration of the trial substance.

Categorization of Adverse Events

The severity of AEs will be categorized based on the National Cancer Institute Common Terminology Criteria for Adverse Events (CTCAE) Version 5.0 as follows:

- **Grade 1 Mild:** Asymptomatic or mild symptoms; clinical or diagnostic observations only; intervention not indicated
- **Grade 2 Moderate:** Minimal, local, or noninvasive intervention indicated; limiting age-appropriate instrumental Activities of Daily Living (ADL)*
- **Grade 3 Severe or medically significant but not immediately life-threatening:** Hospitalization or prolongation of hospitalization indicated; disabling; limiting self-care ADL**
- Grade 4 Life-threatening consequences: An event that puts the subject at immediate risk of death
- **Grade 5:** Death related to AE.

Note: Not all grades are appropriate for all AEs. Therefore, some AEs are listed within the CTCAE with fewer than 5 options for grade selection. Grade 5 (death) is not appropriate for some AEs and therefore is not an option. * Instrumental ADL refer to preparing meals, shopping for groceries or clothes, using the telephone, managing money, etc. **Self-care ADL refer to bathing, dressing and undressing, feeding self, using the toilet, taking medications, and not bedridden. The Investigator (or designee) will make a determination of the relationship of the AE to the study drug using a 2-category system according to the following guidelines:

- **NOT RELATED** = The time course between the administration of investigational product and the occurrence or worsening of the AE rules out a causal relationship and another cause (eg, concomitant drugs, therapies, complications, comorbidities) is suspected
- **RELATED** = The time course between administration of investigational product and the occurrence or worsening of the AE is consistent with a causal relationship and no other cause (eg, concomitant drugs, therapies, complications, comorbidities) can be identified.

An AE is associated with the use of the drug if there is a reasonable possibility that the experience may have been caused by the drug.

Pregnancy

As information is available, a pregnancy in female partners of male subjects diagnosed through EOS or ET (if the subject discontinues from the study and does not complete a Follow-up Phone Call) and for up to 90 days after study drug administration should be reported by the Investigator (or designee) via email to Covance or the Sponsor's Clinical Safety Representative within 24 hours of first awareness. Covance or the Sponsor's Clinical Safety Representative will then forward the Pregnancy Form to the Investigator (or designee) for completion.

email: [contact]

If possible, the subject's partner should be followed by the Investigator (or designee) until completion of the pregnancy. If the pregnancy ends for any reason before the anticipated date, the Investigator (or designee) should notify Covance or the Sponsor's Clinical Safety Representative. At the completion of the pregnancy, the Investigator (or designee) will document the outcome of the pregnancy.

Subjects will be instructed to notify the Investigator immediately if they discover their sexual partner is pregnant. In this instance, the subject's partner must provide written consent before pregnancy information can be collected. When a CRU becomes aware that the female partner of a male subject is pregnant, they are to contact the Investigator (or designee) immediately (within 24 hours of the CRU staff becoming aware of the event) in addition to notifying Covance or the Sponsor's Clinical Safety Representative via email.

All pregnancies should be recorded on the required pregnancy forms.

Definition of Serious Adverse Events

An SAE (by FDA definition) is any adverse drug experience occurring at any dose that results in any of the following outcomes:

• Death;

- A life-threatening adverse drug experience (ie, one that places the subject, in the view of the Investigator [or designee], at immediate risk of death);
- Inpatient hospitalization or prolongation of existing hospitalization;
- A persistent or significant disability/incapacity;
- A congenital anomaly/birth defect;
- An important medical event that may require medical or surgical intervention to prevent one of the above outcomes.

Important medical events that may not result in death, be life-threatening, or require hospitalization may be considered SAEs when, based on appropriate medical judgment, they may jeopardize the patient or subject and may require medical or surgical intervention to prevent one of the outcomes listed in this definition.

Unexpected Adverse Drug Reaction

An AE or suspected adverse drug reaction is considered 'unexpected' if the event is not listed in the Reference Safety Information section of the IB or if it is not listed at the specificity or severity that has been observed for an unapproved IMP.

Reporting

Food and Drug Administration-reportable AEs are AEs that are associated with the use of the drug and represent events that are assessed as serious, related, and unexpected. Food and Drug Administration-reportable AEs will be reported by the CRU to the Sponsor and the responsible IRB. Final determination of whether an event represents a SUSAR will be the responsibility of the Sponsor.

Within 24 hours of when an AE that is potentially FDA-reportable is first recognized or reported, and within 24 hours of any SAE (regardless of whether the event is assessed as related or unrelated to study drug) being first recognized or reported, Covance or the Sponsor's Clinical Safety Representative will be notified by the Investigator (or designee) in writing using the following email address:

email: [contact]

To report the SAE, the completed report form should be sent by email to Covance or the Sponsor's Clinical Safety Representative within 24 hours of awareness. Incoming reports are reviewed during normal business hours. Additional reporting instructions and the SAE Report Form are provided in the Study Manual.

The IRB will be notified of any FDA-reportable AE within the timeframe required by the IRB. The IRB Serious and Unexpected Adverse Experience Submission Form will be completed and submitted with the copy of the written confirmation or summary of the AE.

Clinical Chemistry Panel (Fasted):	Hematology Panel:	
Alanine aminotransferase (ALT)	Hematocrit	Coagulation Parameters:
Albumin Alkaline phosphatase (ALP) Amylase Aspartate aminotransferase (AST) Bilirubin (direct and total) Blood urea nitrogen Calcium Chloride Cholesterol Creatine kinase Creatinine Glucose Iron	Hemoglobin Mean corpuscular hemoglobin Mean corpuscular hemoglobin concentration Mean corpuscular volume Platelet count Red blood cell (RBC) count RBC distribution width White blood cell (WBC) count WBC differential (percent and absolute): Basophils Eosinophils Lymphocytes	Partial thromboplastin time Prothrombin time International normalized ratio Serology: ^b Human immunodeficiency virus (HIV) antibody Hepatitis B surface antigen (HBsAg) Hepatitis B virus (HBV) core antibody Hepatitis C virus (HCV) antibody
Lipase	Monocytes	antioody
Magnesium	Neutrophils	
Phosphorus Potassium	Urinalysis:	Other Tests:
Sodium Total protein Triglycerides Uric acid	Bilirubin Color and appearance Glucose Ketones	Hemoglobin A1c (HbA1c) ^b Estimated glomerular filtration rate ^{a,c} Thyroid-stimulating hormone
Urine Drug Screen: ^a	Leukocyte esterase Nitrite	(TSH) ^b SARS-CoV-2 (COVID-19) test
Including but not limited to the following: Alcohol (ethanol) Amphetamines Barbiturates Benzodiazepines Cannabinoids Cocaine (metabolite) Methadone Opiates Phencyclidine Cotinine	Occult blood pH and specific gravity Protein Urobilinogen Microscopic examination including bacteria, casts, crystals, epithelial cells, RBCs, and WBCs (if protein, leukocyte esterase, nitrite, or blood is positive)	5AK5-C0 v -2 (CO v ID-13) test

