## 8.6. Safety and Tolerability Assessments

### 8.6.1. Adverse Events

All AEs will be coded using the Medical Dictionary for Regulatory Activities (MedDRA) Version 23.0. All AEs will be assigned severity grade using National Cancer Institute Common Terminology Criteria for Adverse Events (CTCAE) Version 5.0.

A treatment-emergent adverse event (TEAE) will be defined as an AE that starts during or after the first dose, or starts prior to the first dose and increases in severity after the first dose.

A treatment-related TEAE will be defined as a TEAE with a relationship of related to the study treatment, as determined by the investigator.

All AEs will be listed. In addition to the data recorded in the database, the listings will include derived onset time and duration. Onset time will be calculated from the time of dosing for TEAEs only.

The frequency of subjects with TEAEs and the number of TEAEs will be summarized by part for the following categories:

- TEAEs (overall, serious, leading to discontinuation, and leading to death) by part
- TEAEs by severity and part
- Treatment-related TEAEs (overall, serious, leading to discontinuation, and leading to death) by part
- Treatment-related TEAEs by severity and part

The frequency of subjects will be summarized separately for TEAEs and treatment-related TEAEs by the following:

- System organ class and preferred term
- Preferred term and treatment/part
- System organ class, preferred term, day of onset, and treatment/part

For the AE data the following rules will apply:

- For the derivation of TEAE status: If the start date/time of an AE is incomplete or missing, an AE will be assumed to be a TEAE, unless the incomplete start date/time or the end date/time indicates an AE started prior to dosing.
- For the derivation of treatment-related TEAE status: If the study treatment relationship for a TEAE is missing, a TEAE will be assumed to be a treatment-related TEAE.

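### Protocol Appendix 1's two causality categories are not exhaustive: an AE with consistent timing and another identifiable cause is neither RELATED nor NOT RELATED

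*Protocol*

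**What the plan says.** Protocol Appendix 1 (Categorization of Adverse Events) says that the Investigator "will make a determination of the relationship of the AE to the study drug using a 2-category system according to the following guidelines". Two definitions follow:

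- **NOT RELATED:** the time course "rules out a causal relationship and another cause (eg, concomitant drugs, therapies, complications, comorbidities) is suspected".
- **RELATED:** the time course "is consistent with a causal relationship and no other cause (eg, concomitant drugs, therapies, complications, comorbidities) can be identified".

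The next sentence introduces another term: "An AE is associated with the use of the drug if there is a reasonable possibility" that the drug caused it. Under Reporting, the same appendix describes FDA-reportable AEs as "AEs that are associated with the use of the drug and represent events that are assessed as serious, related, and unexpected".

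The category is then used in three places:

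- SAP 8.6.1: "A treatment-related TEAE will be defined as a TEAE with a relationship of related to the study treatment, as determined by the investigator". A missing relationship is counted as related.
- Protocol 8.4 presents AE incidence by relationship.
- Protocol 3.1 and 7.2.1 limit AE reporting between End of Treatment (EOT) or Early Termination (ET) and End of Study (EOS) to AEs judged related. SAEs are reported whatever their cause.

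**The concern.** A two-way classification works only if the second category is the complement of the first. Here each category joins two conditions with *and*, so failing one does not put an event in the other. The case left over is an ordinary one: the timing fits the drug, but something else could also explain the event. Subjects in this study fast around dosing, go without caffeine, eat a high-fiber diet and have repeated blood draws (Protocol 5.2, 6.2, Appendix 4). A headache, bowel complaint or venipuncture-site event could fall there. These are illustrations; the documents give no frequency.

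At stake are the treatment-related TEAE tables and, after EOT or ET, whether a non-serious event is reported at all. Events before EOT or ET stay in the listings whatever their label. An event left unreported after that point cannot be recovered from any later listing.

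**Working it through.** The plan states no figure here, so the check is logical: apply the two definitions literally to each combination of timing and other cause. The definitions use different words for the other cause (*suspected* in NOT RELATED, *can be identified* in RELATED), so cause needs three levels.

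| Timing | No other cause | Suspected only | Identified |
|---|---|---|---|
| Ruled out | neither | NOT RELATED | NOT RELATED |
| Consistent | RELATED | RELATED | **neither** |

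Two of the six cells are unassigned. Ruled-out timing with no other cause is a drafting slip without consequence, since such an event is plainly not related. Consistent timing with an identified cause is the substantive gap. The suspected-only cell shows the wording mismatch: a suspected cause supports NOT RELATED when timing is ruled out, but does not defeat RELATED when timing is consistent.

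**Does another sentence fill the gap?** The reasonable-possibility sentence defines *associated*. The Reporting text then lists *associated* and *related* as separate requirements and does not say that one implies the other. The SAP's missing-relationship rule covers a blank field, not an event that fits neither definition.

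**Size.**

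- Let r be the clearly related events and k those in the gap. The number classed as related lies between r and r + k. The documents do not give k. The tabulated rise can be less than k, because SAP 8.6.1 counts repeats of a preferred term in a subject once per treatment.
- One subject whose only candidate related TEAE is in the gap moves the treatment-related frequency by 1/6 = 16.7 percentage points, or 1/7 = 14.3 if one replacement is also dosed.
- SAP 8.6.1 lists 4 overview summaries (2 treatment-related) and 3 breakdowns, each produced for all TEAEs and for treatment-related TEAEs (3 × 2 = 6, of which 3 treatment-related). So (2 + 3) of (4 + 6), or 5 of 10 summary types, depend on the category. This counts table types, not size of effect.
- The restricted reporting window is 7 ± 2 days (Protocol 7.2.1), so 5 to 9 days. After EOT it opens no earlier than about 264 h (Part 1) or 192 h (Part 2) after dosing. At the half-life of roughly 20 h in Protocol 1.3.2, that is 264/20 = 13.2 and 192/20 = 9.6 half-lives. That half-life comes from patients, with an imputed 24-hour value. After ET the window can open earlier.

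**The case against.** The strongest reply is that the definitions are called guidelines, that the reasonable-possibility sentence directly follows them, and that a sensible Investigator would treat it as the overall test. That is a natural reading and it softens the gap. It does not close it: the sentence is attached to another term, the Reporting text keeps the two terms apart, and two Investigators could code the same event differently without departing from the text.

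Three stronger readings are tempting and are not supported:

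- *Any possible alternative cause excludes RELATED.* It does not. RELATED fails only when another cause can be identified.
- *Related events will be under-counted.* That assumes gap events default to NOT RELATED. No document sets that default; NOT RELATED is just as strict, because the timing must exclude causation. A blank relationship counts as related.
- *The follow-up call will miss these events because it asks only about SAEs and drug-related AEs.* Protocol 7.2.1 states the purpose of the call in those terms, but Appendix 4 schedules the non-leading health inquiry and AE collection at that contact in both parts. The event may be elicited; it is the reporting that causality filters.

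The population also narrows exposure: healthy subjects, with most medication prohibited (Protocol 3.2, 6.1). The listed alternative causes are only examples, however, so the risk is reduced and not removed.

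**Conclusion.** Wrong as written, minor severity. The definitions leave a foreseeable class of AE unassigned while requiring an assignment. The consequence is indeterminate classification, with net direction and size unknown; the 16.7-point figure is what one subject is worth in a part of six, not an estimate of bias.

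A reader might infer that safety reporting of serious events is compromised. The documents do not support that. All SAEs are notified within 24 hours "regardless of whether the event is assessed as related or unrelated to study drug", and "Final determination of whether an event represents a SUSAR will be the responsibility of the Sponsor". All TEAEs are summarized whatever their relationship, and PK and mass-balance results do not depend on the category. What remains is the labelling of AEs in a descriptive secondary outcome, and the reporting of non-serious events after EOT or ET. The conclusion rests on a literal reading of the definitions and on no other available text assigning these events; the Study Manual and any CRF completion guidance were not available.

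**What to change.** In Protocol Appendix 1:

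1. Define RELATED as a reasonable possibility that the study drug caused the event, even if another cause is also possible or has been identified. The last clause is a clarification added to the appendix's own standard.
2. Define NOT RELATED as the absence of such a reasonable possibility. The two categories then cover every event without overlap, and the suspected/identified mismatch disappears.
3. Under Reporting, state that *associated with the use of the drug* and *related* mean the same thing, or keep only one of the terms.

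The cost is two definitions, one sentence and matching CRF completion guidance. The SAP needs no change, because it already takes the Investigator's category as given. The downside is that somewhat more events will be classed as related.
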